4 DETERMINATION OF SAMPLE SIZE

The sample size and design characteristics to test the hypothesis under the primary objective based on the primary endpoint, the ADCOMS at 12 months, were determined by means of simulations. Extensive trial simulations have shown that a total of 800 subjects will be sufficient to demonstrate that the most likely ED₉₀ dose achieves a clinically significant difference (CSD) from placebo with a probability of at least 95% in the interim analyses and greater than 80% in the analysis at 12 months if the trial does not stop for early

success. With 800 subjects, the average probability of study success is 80% across a wide range of dose response scenarios, and there is at least 80% probability of study success for the dose response scenarios where the treatment is considered to show a clinically significant difference from placebo as defined in the Protocol. Simulations have also shown that if there is no efficacy at all for any dose, then the probability of falsely claiming superiority to placebo is no more than 10% assuming a 20% dropout rate.

For each of the 6 treatment groups (5 active dose regimens and placebo) the final number of subjects per group will differ depending on the observed interim treatment responses. The simulation plan is described in the appendix section of this document which presents further details.

vMRI

The null hypothesis is that there is no difference between active dose and placebo. There are 5 null hypotheses corresponding to 5 active dose regimens. The alternative hypothesis is that at least 1 null hypothesis is false (1-sided). The null hypotheses will be tested using Dunnett-Hsu method with 1-sided alpha of 0.05. The statistical power was estimated through simulation for a moderate dose-response assumption that the percent reduction in change from baseline of total hippocampal volume compared to placebo would be 15%, 20%, 25%, 15%, and 20% corresponding to the 5 dose regimens (2.5, 5, and 10 mg/kg biweekly, 5 and 10 mg/kg 4-week interval), respectively. The estimated power for actual planned study sample size is 76.4% at 12 months and 69.4% at 18 months, assuming an attrition rate of 20% at 12 months and an exponential dropout model. Under a stronger dose-response assumption (ie, the percent reduction in change from baseline of total hippocampal volume compared to placebo is twice as much as that in the moderate dose-response assumption), the estimated power is at least 99% at both 12 and 18 months.

AMYLOID PET (IMAGING SUBGROUP)

The null and alternative hypotheses and statistical test are the same as that for vMRI. To estimate the sample size for amyloid PET imaging subgroup at 18 months, a common standard deviation of change from baseline was estimated as 0.4 and a reasonable mean difference between treatment and placebo was estimated as 0.25 (SUVR). The corresponding standard deviation and mean difference at 12 months were estimated as 0.27 and 0.17, respectively. Assuming a moderate dose-response that the best dose regimen would achieve a difference of 0.25 (SUVR), and that the 2 middle and 2 low dose regimens would achieve a difference of 0.2 and 0.15 (SUVR), respectively, it would require a total of 230 subjects from all 6 arms at 18 months to achieve an 80% power. This sample size took into account possible unequal number of subjects per arm. Under the same attrition rate assumption as that for vMRI, a total sample size of 306 is required at 12 months in order to target 230 subjects at 18 months. The estimated power with 306 subjects at 12 months is approximately 85%. Because amyloid PET imaging is required for every subject at baseline, the post baseline amyloid PET in the imaging subgroup will be planned for the first 306 subjects who have consented and who are still on treatment at 12 months.

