1.0 INTRODUCTION

This is a phase II dose-finding study of BAN2401 for the treatment of Alzheimer's disease. The minimum sample size will be 196 patients and the maximum sample size will be 800 patients. We use response adaptive randomization to allocate patients between placebo control and 5 active doses with the goal of characterizing the dose response curve. The study will be monitored for early success and early futility. There are two schedules of administration, bi-weekly and once monthly. The primary endpoint is the change in a composite clinical score from baseline to 52 weeks. A difference from control of at least 0.03 would be considered a clinically significant difference (CSD).

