2.2 Dose-Response Model Primary

We label the mean change from baseline to 52-weeks for dose group d as θ_d . We construct a dose-response model for the mean change from baseline for each treatment arm. The arms are modeled with a two-dimensional first-order normal dynamic linear model (NDLM). This model is a Gaussian random walk model. The structure is

$$\begin{aligned} [\theta_0] &\sim N(0, 0.5^2) \\ [\theta_1] &\sim N(0, 0.5^2) \end{aligned}$$

□

and the NDLM structure for the bi-monthly doses:

$$[\theta_2] \sim N(\theta_1, \tau^2)$$

□

$$[\theta_3] \sim N(\theta_2, \tau^2)$$

The monthly doses are “connected” to the dose-response model through the respective bi-monthly doses. The connection through the NDLM first order structure results in the following priors

$$[\theta_4] \sim N(\theta_2, \tau^2)$$

and

$$[\theta_5] \sim N\left(\frac{\theta_3 + \theta_4}{2}, \frac{\tau^2}{2}\right).$$

The drift parameter (variance component), τ^2 is modeled with the following prior distributions:

$$[\tau^2] \sim IG(0.25, 0.0025)$$

where $IG(a, b)$ is the inverse gamma distribution with shape parameter a and scale parameter b . This prior has the equivalent weight of 0.5 observations worth of weight that the value of τ is 0.1.

The prior distribution on the initial dose is selected to be a vague prior. An effect size of 0.03 is considered clinically significant and the standard error of the clinical scale is 0.15. Therefore these priors are quite weak and allow the data to shape the dose-response model. The prior for the “drift parameter” is selected to have minor weight that there will be similarity across the doses, and hence a minor amount of borrowing. With 5 doses the amount of borrowing is determined largely by the similarity in outcomes across doses.

The distribution of the variance of the primary endpoint, σ^2 , is modeled with the following prior:

$$[\sigma^2] \sim IG(2.5, 0.056).$$

The prior is equivalent to a prior weight of 5 observations worth of information that the value of σ is 0.15. The value of 0.15 is based on initial modeling by Eisai. This prior allows the historical data estimate of 0.15 to have some role in the early part of the trial. When 300 subjects have been enrolled this prior will have a very minor role (5/305 weight is less than 2%).

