9.0 OPERATING CHARACTERISTICS

Table 9.1 shows the probabilities of trial success and futility and the mean total sample size for each scenario shown in Table 8.2. We present operating characteristics assuming the linear longitudinal profile and a 40% dropout rate at 52 weeks. Operating characteristics based on the late onset and symptomatic longitudinal profiles are shown in the appendix. Operating characteristics based on the linear longitudinal profile but assuming a lower (20% and 30%) dropout rate at 52 weeks are also shown in the appendix. Results are similar across the three longitudinal profiles and the three dropout rates.

We show the probability of early success, probability of early futility, the probability the trial continues to completion (complete accrual and complete follow-up) and the total probability of trial success (either early or at trial completion).

Scenario		Mean N	Pr(Stop Early Success)	Pr(Stop Early Futility)	Pr(Go To Trial Completion)	Pr (Success)
1	Null	683.1	0.119	0.447	0.433	0.125
2	Small Effect	697.4	0.281	0.157	0.562	0.353
3	BM Good	656.7	0.660	0.044	0.296	0.801
4	Q Low	573.1	0.962	0.019	0.019	0.978
5	Both Good	562.4	0.970	0.010	0.019	0.987
6	U-Shape Good	582.9	0.921	0.012	0.067	0.972
7	U-Shape Low	646.4	0.684	0.035	0.280	0.817
8	Small Increases	612.1	0.831	0.019	0.150	0.927
9	One Works	668.5	0.544	0.121	0.335	0.692
10	All 0.04	654.2	0.612	0.042	0.346	0.748
11	All 0.06	592.2	0.897	0.013	0.090	0.961
12	All 0.08	535.9	0.986	0.005	0.010	0.994
13	Medium Effect	683.1	0.416	0.090	0.495	0.537

We evaluate Type I error by the probability of trial success in the scenario that there is no treatment effect. In the “Null” scenario, there is a 12.5% probability of trial success. This is the one-sided Type I error rate of this trial.

We evaluate power by the probability of trial success in alternative scenarios. For example, in scenarios where all doses are better than control by at least the CSD, such as “U-Shape Good” or “Small Increases” there is greater than a 90% probability of trial success. In the “Small Effect” scenario, there is only a 35% probability of trial success, but the treatment effect for each dose is at or below the clinically significant difference.

Table 9.2 shows the mean and standard deviation of the number of patients allocated to each treatment arm. The true ED₉₀ for each scenario is shown in bold italics. The true ED₉₀ dose tends to receive the greatest number of patients in each scenario.

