10.0 CONCLUSIONS

With a minimum of 196 and a maximum of 800 patients, this design has a one-sided Type I error rate of approximately 12.5% and a high probability (at least 80%) of success for many scenarios in which the treatment would be considered effective. Adaptive allocation tends to allocate the greatest number of patients to the true ED₉₀ and the true ED₉₀ has a high probability of being identified for consideration in a future phase III trial.

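### Section 4 claims at least 80% success wherever the drug shows a clinically significant difference, but the SAP's own tables give 75–77% for 'All 0.04' and 69–76% for 'One Works'

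*SAP*

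**What the plan says.** SAP Section 4 makes three claims from the simulations:

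- On average, "the average probability of study success is 80% across a wide range of dose response scenarios".
- For effective treatments, "at least 80% probability of study success for the dose response scenarios where the treatment is considered to show a clinically significant difference from placebo". The sentence goes on to refer to the protocol for the definition.
- Under no effect, the false-positive probability is "no more than 10% assuming a 20% dropout rate".

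Section 4 sends the reader to the simulation plan in Appendix 13.2 for detail. That plan's introduction fixes the threshold: "A difference from control of at least 0.03 would be considered a clinically significant difference (CSD". The same 0.03 is built into its futility and success rules (Sections 5.1 to 5.3). Section 9.0 says of scenarios in which all doses beat control by at least the CSD, naming U-Shape Good and Small Increases as examples, that "there is greater than a 90% probability of trial success". Section 10.0 is more cautious than Section 4: it claims a success probability of at least 80% only for many of the effective scenarios.

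**The concern.** The Section 4 sentence covers every scenario in which the treatment shows a CSD. Some scenarios in Table 8.2 meet that description on the plan's own threshold, yet their tabulated success probability is below 80%.

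Section 4 is the sample-size justification for the primary endpoint, and a reader will use it to judge how much a result that misses the 12-month criterion counts against the drug. At 80% or better, a true CSD is missed in at most 20% of trials. For 'All 0.04' the tables imply a miss in 23.2% (1 − 0.768, 20% dropout) to 25.2% (1 − 0.748, 40% dropout). For 'One Works' it is 24.0% to 30.8%.

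**Working it through.** The claimed figure comes from simulation, so the check is to read the tables against the scenario definitions.

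**Inputs.** CSD 0.03 (Appendix 13.2, Section 1.0). True effects by dose (Table 8.2). Probability of success from Table 9.1 (linear profile, 40% dropout), from the two dropout appendix tables (linear, 20% and 30%), and from the late-onset and symptomatic appendix tables.

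**Claims that reproduce.** The null row of the 20% dropout table is 0.10, which matches Section 4's type I error statement. The average over the 12 non-null scenarios is 9.953 / 12 = 0.829 at 20% dropout, 9.767 / 12 = 0.814 at 40% dropout and 9.618 / 12 = 0.80 under late onset. The average claim therefore holds.

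**Which scenarios show a CSD.** Success is judged on the ED90 dose, the simplest dose with at least 90% of the largest effect.

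- All 0.04: every dose is 0.04, above 0.03 on any reading.
- One Works: 10 mg/kg biweekly is 0.06 and the rest are 0. The ED90 dose is at 0.06 / 0.03 = 2 times the CSD.
- Medium Effect: effects are 0.015, 0.03, 0.04, 0.015 and 0.03. Since 90% of 0.04 is 0.036, the ED90 dose is the one at 0.04, above the CSD. Two doses sit exactly on the CSD and two are below it.

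**Tabulated probability of success.**

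| Scenario | 20% dropout | 30% dropout | 40% dropout | Late onset | Symptomatic |
|---|---|---|---|---|---|
| All 0.04 | 0.768 | 0.757 | 0.748 | 0.734 | 0.738 |
| One Works | 0.760 | 0.732 | 0.692 | 0.678 | 0.722 |
| Medium Effect | 0.538 | 0.528 | 0.537 | 0.528 | 0.501 |

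**Shortfall from 0.80, linear profile, at 20% / 30% / 40% dropout.**

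- All 0.04: 0.032 / 0.043 / 0.052
- One Works: 0.040 / 0.068 / 0.108
- Medium Effect: 0.262 / 0.272 / 0.263

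The most favourable basis is 20% dropout, which is also the one Section 4 names for its type I error. No scenario in the table above reaches 0.80 there or anywhere else.

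**The other effective scenarios.** BM Good, Q Low, Both Good, U-Shape Good, U-Shape Low, Small Increases, All 0.06 and All 0.08 all reach 0.80 under the linear profile at each dropout rate. The lowest is BM Good, at 0.801 with 40% dropout. Under late onset, BM Good (0.773) and U-Shape Low (0.796) also fall below 0.80.

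**Section 9.0.** Seven scenarios have every dose at or above 0.03. Their Table 9.1 values are: Both Good 0.987, U-Shape Good 0.972, U-Shape Low 0.817, Small Increases 0.927, All 0.04 0.748, All 0.06 0.961 and All 0.08 0.994. Five of the seven exceed 0.90. U-Shape Low and All 0.04 do not.

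**The case against.** The best defence is that Section 4 leaves the definition to the protocol, which is not shown, and that the SAP never lists the scenarios that count. If every dose must show a CSD, as the wording of Section 9.0 suggests, then One Works and Medium Effect drop out. That leaves All 0.04, whose gap at 20% dropout is 3.2 points. A reading that required every dose to exceed a CSD set above 0.04 would remove all three. That much is fair, and Medium Effect is the most arguable of the three. But the simulations that Section 4 cites use 0.03 throughout, and on 0.03 All 0.04 fails even the strictest reading. One Works is hard to exclude when success is judged on the ED90 dose.

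It is also fair that the appendix prints every value, that Section 10.0 is properly qualified, and that the Section 9.0 sentence is phrased as an example whose two named scenarios do exceed 90%. The fault in Section 9.0 is loose wording.

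A reader might go further in three ways that the documents do not support.

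- *That the whole power justification fails.* It does not: the average claim holds and eight effective scenarios reach 80% under the linear profile.
- *That Section 10.0 is wrong to say the true ED90 "has a high probability of being identified for consideration in a future phase III trial".* The phrase is qualitative. Applying the plan's ED90 rule to Table 8.2, the true ED90 has the highest entry in all 12 non-null rows of Tables 9.3 and 9.5. In the three scenarios with equal effects, choosing another dose loses no efficacy.
- *That the tables predate the restriction on APOE4 carriers.* Nothing dates the simulations. At most, the allocation rule in Section 4.0 of the simulation plan shows no split by APOE4 status.

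**Conclusion.** Wrong as written. With the SAP's own CSD of 0.03, the Section 4 minimum of 80% is not a property of the simulated design. Under the linear profile, success is 75–77% for All 0.04 and 69–76% for One Works, depending on dropout. It is 53–54% for Medium Effect if a CSD for the best dose is what counts. The undisputed part, All 0.04 at 20% dropout, is a modest 3.2 points. The miss recurs in all five tables, so it does not depend on the choice of dropout rate or longitudinal profile. The conclusion rests on the tables as printed and on 0.03 as the CSD; the design was not re-simulated. It concerns the stated power only and says nothing about whether 800 subjects was an adequate choice.

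**What to change.** In Section 4, replace the universal statement with one claiming at least 80% for many of the scenarios, and give the tabulated values with their basis (linear profile, 20–40% dropout):

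- at least 80% for BM Good, Q Low, Both Good, U-Shape Good, U-Shape Low, Small Increases, All 0.06 and All 0.08;
- 75–77% for All 0.04;
- 69–76% for One Works;
- 53–54% for Medium Effect.

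Add that under late onset BM Good (77.3%) and U-Shape Low (79.6%) also fall below 80%. In Section 9.0 of the simulation plan, limit the sentence about success above 90% to the scenarios that meet it. Section 10.0 needs no change on this point. If the APOE4 restriction is mentioned at all, say only that the simulated allocation rule shows no APOE4 split.

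The cost is a text edit. The stated power becomes less favourable.

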6.0 ACCRUAL AND DROPOUT

We assume accrual will increase at a constant rate over the first 6 months of the study to a peak accrual rate of 32 patients per month. The table below shows the approximate accrual rate at each month during the 6 month ramp-up to the steady state accrual rate of 32 patients per month.

Accrual Ramp-Up: Patients per Month	
Week	Patients Per Month
1	5.33
2	10.66
3	16
4	21.33
5	26.66
6	32
Steady State Patients per Month from 6 Months	32

We assume an exponential rate of dropout such that 22% of patients have dropped out by 26 weeks and 40% have dropped out by 52 weeks. As a sensitivity analysis we also consider dropout rates of 20% and 30% by 52 weeks.

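### SAP Section 4 states the vMRI Dunnett-Hsu power only at 20% attrition, although Appendix 13.2 takes 40% dropout by 52 weeks as its base case; at 40% that power would be roughly 65% at 12 months and 53% at 18 months, counting completers only

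*SAP*

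**What the plan says.** **Section 4, vMRI.** Five active regimens are each compared with placebo: "The null hypotheses will be tested using Dunnett-Hsu method with 1-sided alpha of 0.05". The assumed reductions in hippocampal volume change "would be 15%, 20%, 25%, 15%, and 20% corresponding to the 5 dose regimens". Power is the chance of rejecting at least one of the five null hypotheses. The result: "The estimated power for actual planned study sample size is 76.4% at 12 months and 69.4% at 18 months, assuming an attrition rate of 20" per cent at 12 months, with an exponential dropout model. If the effects are twice as large, "the estimated power is at least 99% at both 12 and 18 months".

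**Section 4, amyloid PET.** The text relies on the same attrition assumption as vMRI to go from 306 subjects at 12 months to 230 at 18 months.

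**Section 4, primary endpoint.** The statement that the false-positive probability is at most 10% is also made at 20% dropout.

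**Appendix 13.2, Section 6.0.** Dropout is exponential, with 22% lost by 26 weeks, and "40% have dropped out by 52 weeks". Then: "As a sensitivity analysis we also consider dropout rates of 20% and 30% by 52 weeks". The main operating characteristics in Appendix 13.2, Section 9.0, are at 40%. Results at 20% and 30% are in a separate appendix on dropout rates.

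**The concern.** One trial of 800 subjects carries two planning rates for dropout, one twice the other, and the SAP does not say why. The rate used for vMRI is the lowest that the simulation plan considers. The vMRI power is shown at that rate alone, whereas the primary endpoint's operating characteristics are shown at 20%, 30% and 40%.

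Hippocampal volume is a key secondary endpoint at 18 months and a secondary endpoint at 12 months. Section 5.4.4 says that Dunnett-Hsu adjusted p-values will be reported for vMRI. A reader who weighs a non-significant adjusted p-value against 69% power would over-read it if retention were closer to the appendix's base case.

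**Working it through.** **1. Subjects remaining.** With exponential dropout, retention at 18 months is the 12-month retention to the power 1.5.

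| 12-month dropout | N at 12 months | N at 18 months |
|---|---|---|
| 20% | 800 × 0.80 = 640 | 800 × 0.80^1.5 = 572 |
| 40% | 800 × 0.60 = 480 | 800 × 0.60^1.5 = 372 |

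The 18-month figure in Section 4 thus rests on 572/372 = 1.54 times as many subjects as the appendix's base case would leave.

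**2. The stated power.** It cannot be reproduced from the SAP's own inputs, because neither the placebo change in hippocampal volume nor its SD is given. The one unknown, placebo change divided by SD, was therefore solved at each time point so that 640 subjects give 76.4% and 572 give 69.4%. The test was the one-sided Dunnett maximum at 0.05, with effects of 15, 20, 25, 15 and 20% and 400,000 normal draws. The critical value was 2.23 to 2.29, depending on allocation. With 4:2:2:2:2:2 allocation the solved ratios are about 1.21 and 1.18. The two stated figures are roughly coherent: the 12-month ratio carried to 18 months would give about 72%, against 69.4%.

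**3. Power at other dropout rates, with the solved effects held fixed (completers only).**

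| 12-month dropout | 12 months | 18 months |
|---|---|---|
| 20% (as stated) | 76.4% | 69.4% |
| 30% | about 71% | about 61% |
| 40% | about 65% | about 53% |

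At 40%, the range over seven allocations is 64.1 to 65.0% at 12 months and 51.5 to 52.7% at 18 months. The allocations were 4:2:2:2:2:2, equal, four splits from Table 9.2 of Appendix 13.2, and one extreme split. Allocation matters little because the ratio of retained subjects drives the result.

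**4. Hand check with a single comparison, one-sided 0.05.**

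- 12 months: (0.719 + 1.645) × √0.75 = 2.047; minus 1.645 leaves 0.402; power 65.6%.
- 18 months: (0.507 + 1.645) × 0.75^0.75 = 1.734; minus 1.645 leaves 0.09; power 53.6%.

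**5. Strong effect.** With the effects doubled and 40% dropout, completers-only power is about 99.5% at 12 months and about 97% at 18 months (97 to 98% over the allocations).

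**6. If earlier scans count.** vMRI is taken at 6, 12 and 18 months, and the planned MMRM uses scans made before dropout. The within-subject correlation is not given, so 0.5 to 0.9 was assumed (constant or decaying with time), and the back-solve was repeated with the information from partial data retained. Power at 40% dropout is then about 66 to 69% at 12 months and 54 to 61% at 18 months. Strong-effect power at 18 months is about 98 to 99%.

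**7. The amyloid PET step.** Six months of exponential dropout at 20% a year leaves 306 × √0.80 = 274 subjects, not 230. Working back, 230/√0.80 = 257 would be needed at 12 months, not 306. At 40% a year, 306 × √0.60 = 237. The stated step is closer to the 40% rate than to the 20% rate that it cites.

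**The case against.** Five points can be made on the other side.

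- **The condition is stated openly.** Section 4 says that the power is at 20% attrition, and nothing shows 76.4% or 69.4% to be miscalculated on that basis. This stands. A reader might infer an arithmetic error, but with no placebo change or SD in the SAP there is no ground for that.
- **Section 4 uses 20% elsewhere too.** Its 10% false-positive figure matches the appendix's 20% row (0.10), not the 40% row (0.125). This also stands. The conflict lies between Section 4 and Appendix 13.2, not within the vMRI paragraph, and the document does not settle which rate is right. Using the rate twice does not explain it, however, and the PET step does not follow from it.
- **The power belongs to a supplementary test.** Under Sections 5.3.3 and 5.4.4 the key secondary comparison is the combined 10 mg groups against placebo. The five-arm Dunnett-Hsu p-value is given in addition. It is tempting to say that the key secondary hippocampal test has only even odds of success. The SAP does not support that, since neither 69% nor 53% is the power of that comparison.
- **Completers-only counting overstates the loss.** Under the correlations assumed in step 6, the 18-month loss is about 8 to 15 points instead of about 17. This stands as a qualification, but the SAP does not say whether its own simulation used the MMRM.
- **Little turns on it.** The 800 subjects were set by the primary-endpoint simulations, and this SAP version dates from June 2018, after the 12-month post-accrual interim report of December 2017. No test or decision rule changes. What changes is how the stated power should be read.

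**Conclusion.** The inconsistency is real. Section 4 and Appendix 13.2 plan the same trial with different dropout, and the vMRI power is shown only under the more favourable rate. The counts of 480 and 372 in place of 640 and 572 follow directly from the SAP's own inputs.

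The fall in power to about 65% at 12 months and 53% at 18 months (about 71% and 61% at 30% dropout) rests on two things: back-solving the undisclosed effect from the stated power, and counting completers only. If earlier scans contribute, the 18-month figure is more like 54 to 61%. On completers, the strong-effect claim of at least 99% does not hold at 18 months under 40% dropout (about 97%). With highly correlated scans it could just hold.

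This is an unreconciled planning input. It is not a shown miscalculation, and it says nothing about the power of the combined 10 mg comparison. It is worth correcting because these are the only vMRI power figures in the SAP.

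**What to change.** 1. State one dropout assumption for Section 4 and Appendix 13.2, or give the reason why vMRI should be planned at 20%.
2. Rerun the sponsor's own vMRI simulation at the appendix's base case of 40% by 52 weeks, for both the moderate and the strong dose response, and report the result beside the 20% figures. The back-solved values here show the likely size and should not be copied in as replacements.
3. State the placebo change and SD used, and whether the simulation analysed completers or used the MMRM.
4. Correct or explain the amyloid PET step from 306 to 230 subjects, which 20% exponential attrition does not give.
5. Say that the vMRI power refers to the five-arm Dunnett-Hsu test and not to the combined 10 mg versus placebo key secondary comparison.

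The cost is a rerun of an existing simulation and a few lines of text. The stated power becomes less favourable. Sample size, design and analyses stay as they are.
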